1.0 Purpose

This Supplemental Analysis Plan (SAP) describes the statistical methods to be used during the reporting and analysis of data collected for the Clinical Evaluation of the Cochlear Nucleus® CI532 Cochlear Implant in Adults. This supplemental plan should be read in conjunction with the Study Protocol.

2.0 Clinical Study Design Overview

This clinical investigation will be conducted as a multicenter, prospective, nonrandomized, single-subject, repeated-measures design in which each subject serves as his/her own control. This approach accommodates the heterogeneity that characterizes hearing-impaired populations. Blinding procedures are not appropriate for this trial design, as it is not possible to conceal the presence, or absence, of a cochlear implant (CI) system from recipients and/or clinical Investigators.

Subjects in this study will be implanted with the commercially available Nucleus CI532 cochlear implant and fit with the CP1000/Nucleus 7 Sound Processor. All testing will be complete with CP1000/Nucleus 7 Sound Processor.

3.0 Subject Population

Study sites will enroll 100 adult cochlear implant candidates at up to 15 North American cochlear implant centers.

Cochlear Americas will adhere to the National Coverage Determination (NCD) for Cochlear Implantation for enrollment of Medicare beneficiaries into the Clinical Evaluation of the Cochlear Nucleus® CI532 Cochlear Implant in Adults. Specifically, the following NCD criteria will be met:

1. Diagnosis of bilateral moderate-to-profound sensorineural hearing impairment with limited benefit from appropriate hearing (or vibrotactile) aids, defined as test scores of less than or equal to 40% correct in the best-aided listening condition on tape-recorded tests of open-set sentence recognition;
2. Cognitive ability to use auditory clues and a willingness to undergo an extended program of rehabilitation;
3. Freedom from middle ear infection, an accessible cochlear lumen that is structurally suited to implantation, and freedom from lesions in the auditory nerve and acoustic areas of the central nervous system;
4. No contraindications to surgery.

Candidates must also meet the following inclusion and exclusion requirements as stated in the study protocol:

Inclusion Criteria:

1. Adults 18 years or older who have a bilateral postlinguistic sensorineural hearing loss.
2. Limited benefit from amplification as defined by test scores of 40% correct or less in the ear to be implanted and 50% or less in the contralateral ear on a recorded monosyllabic word test
 - I. Consistent with the Minimum Speech Test Battery (2011), it is required that all subjects be evaluated at 60 dBA presentation level.
3. Bilateral moderate sloping to profound hearing loss

4. Minimum of 30 days experience with appropriately fit bilateral amplification, fit using the standardized NAL fitting method
5. Proficient in English
6. Ability to complete testing

Exclusion Criteria:

1. Previous cochlear implantation
2. Pre-linguistically deafened (onset of hearing loss at less than two years of age)
3. Ossification or any other cochlear anomaly that might prevent complete insertion of the electrode array
4. Duration of severe to profound hearing loss greater than 20 years
5. Diagnosis of retro-cochlear pathology
6. Diagnosis of auditory neuropathy
7. Unrealistic expectations on the part of the subject regarding the possible benefits, risks, and limitations that are inherent to the surgical procedure and use of the prosthetic device
8. Unwillingness or inability to comply with all investigational requirements
9. Additional cognitive, medical or social handicaps that would prevent completion of all study requirements

4.0 Data Analyses

4.1 Sample Size Estimate

To calculate the minimum sample size required to reject the null hypothesis (H_0) that “Group mean CNC words scores in the best unilateral listening condition measured at 6 months post sound processor activation will not be superior to the group mean score in the preoperative, best unilateral condition”, the following values were chosen:

- A minimum clinically meaningful difference between pre to post activation at 6 months of 15% for CNC words in quiet, based on clinical consensus.
- An expected standard deviation of difference scores of 22.4% for CNC words in quiet. This SD is based on the estimated standard deviation of difference score data collected in completed clinical studies
- A significance level $\alpha = 0.05$ (two-tailed).
- A desired power of 0.9 i.e. there is 90% chance of detecting a real change between the experimental programs.

Based on these assumptions for words in quiet, a sample size of 26 subjects is required to achieve a power of 90%.

AzBio Sentences in Noise

- To calculate the minimum sample size required to reject the null hypothesis (H_0) that “Group mean AzBio sentence in noise scores (SNR +10) in the best unilateral listening condition measured at 6 months post sound processor activation will not be superior to the group mean score in the preoperative, best unilateral condition”, the following values were chosen:

- A minimum clinically meaningful difference between pre to post activation at 6 months of 15% for sentences in noise, based on previous clinical consensus.
- An expected standard deviation of difference scores of 21.3% for AzBio sentences in noise. This SD is based on previous clinical trial data with newly implanted subjects.
- A significance level of $\alpha = 0.05$ (two-tailed).
- A desired power of 0.9
- Based on these assumptions, a sample size of 24 subjects is required to achieve a power of 90%.

Health Utility Index (HUI)

To calculate the minimum sample size required to reject the null hypothesis (H0) that “Group mean utility score (HUI) at 6 months post sound processor activation will not be superior to the scores measured preoperatively the following values were chosen:

- A minimum clinically meaningful difference between pre to post activation at 6 months of 0.12 utility score
- An expected standard deviation of difference scores of 0.18, this is a conservative value based on the SD of the difference measured after hearing aid fitting
- A significance level of $\alpha = 0.05$ (two-tailed).
- A desired power of 0.9

Based on these assumptions, a sample size of 26 subjects is required to achieve a power of 90%.

A sample size of 100 adult subjects will be enrolled in the clinical investigation, this large sample will allow for additional analyses to be conducted specifically the additional patient reported outcome measures, where a large sample size is typically desired. Additionally the sample size provides greater justification for generalizability to the wider clinical population.

4.2 Study Population

All subjects who are consented and enrolled into the clinical study will constitute the intention-to-treat (ITT) population for the purposes of adverse event reporting. Only subjects implanted with the CI532 and fit with the CP1000/N7 Sound Processor and completed per the protocol will be considered as the completed cases (CC) population and per protocol (PP).

4.3 Determining Efficacy

Efficacy of the Cochlear Nucleus CI532 cochlear implant system will be determined by a comparison of preoperative vs. postoperative outcomes measures. The speech measures for this purpose are the CNC Word Test and the AzBio sentences in noise. The primary and secondary efficacy endpoints will be based on analyses of designated test measures at the 6-month postactivation.

4.3.1 Primary Efficacy Objective

The primary efficacy objective for this study is to understand if cochlear implantation with a Cochlear Nucleus CI532 cochlear implant and the use of the CP1000/N7 sound processor in adult patients results in improved speech understanding at 6 months postactivation, as measured by performance on an open-set word recognition test, in the best unilateral listening condition of the implanted ear.

- On the CNC word measure, the group mean score for best unilateral listening condition at 6 months will be better than the group mean score in the preoperative, unilateral aided condition.

The primary hypothesis to be tested in this analysis is the following: that the 6 month postoperative performance is significantly different from preoperative performance in the treated ear. The null and alternative hypotheses are given below.

H01: $iPost - iPre \leq 0$ versus Ha1: $iPost - iPre > 0$

Where $iPre$ is the CNC word score in quiet obtained with a hearing aid preoperatively in the ear to be implanted, and $iPost$ is the CNC word score in quiet obtained at 6 months post sound processor activation in the treated ear. The test will be based on a one-sample t-test of the paired difference in pre and post results and performed at the one-sided 0.025 alpha level. If there is significant evidence that the assumptions of the t-test do not hold (i.e. $p < 0.05$ from a Shapiro-Wilks test of normality), a Wilcoxon signed rank test will be used.

4.3.2 *Secondary Efficacy Objective*

The secondary efficacy objective will be determined by further comparison of group means for preoperative vs. 6 months postoperative outcome measures in best unilateral as measured by performance on sentence recognition in noise. The speech measure for this purpose is the AzBio sentences in noise at a +10 dB Signal-to-noise-ratio

- On the AzBio sentences-in-noise measure at a +10 SNR, the group mean score for best unilateral listening condition at 6 months will be better than the group mean score in the preoperative, unilateral aided condition.

The hypothesis test is as follows:

H01: $iPost - iPre \leq 0$ versus Ha1: $iPost - iPre > 0$

Where $iPost$ is the post-implant value and $iPre$ is the pre-implant value. Each test will be based on a one sample paired t-test of the difference in pre and post results. All tests will be performed at the one-sided 0.025 alpha level.

An additional secondary objective will be evaluated by comparing of the group mean for preoperative vs. 6 months postoperative health utility outcome as measured on the HUI3.

The hypothesis test is as follows:

H01: $iPost - iPre \leq 0$ versus Ha1: $iPost - iPre > 0$

Where $iPost$ is the post-implant value and $iPre$ is the pre-implant value. Each test will be based on a one sample paired t-test of the difference in pre and post results. All tests will be performed at the one-sided 0.025 alpha level.

Additional supportive efficacy analyses will include:

- An analysis of individual data for speech perception measures (CNC word scores and AzBio Sentences in noise scores) to establish the proportions of those subjects showing a significant

improvement, no change, and a significant decrement in performance. Individual scores obtained at 6 months will be compared with those obtained, on the same measures preoperatively, based on the binomial model (see Thornton and Raffin, 1978). A similar analysis will be completed for data obtained at 3 and 12 months.

Additionally, for the HUI3, the proportion of individual subjects showing significant improvement (i.e. a change pre to 6 months on the multi score of ≥ 0.03) will be reported. For the individual attributes a change pre to 6 months of ≥ 0.05 is considered significant, (Horsman, et al., 2003) The proportion of subjects demonstrating a significant change will be reported.

Both group mean scores and proportion of individual subjects showing significant benefit, no change in performance and significant decrement in performance will be documented and reported in a detailed annual progress report and in subsequent publications.

For all speech perception measures individual data analysis will be performed and reported in a peer reviewed journal and in the Annual Progress Report or presentation.

4.4 Type 1 Error Control

The hypotheses for the primary and secondary Endpoints are to be tested formally according to a fixed sequence testing procedure. This testing procedure is based on the principle of a closed testing procedure and is used to control the type I error. In the fixed sequence testing, all the following superiority tests will be conducted using a two-tailed 95% CI ($\alpha=0.025$ one-sided).

The Primary Endpoint will be tested first. Only if the superiority test for the Primary Endpoint is successful, then the secondary endpoints will be tested. If the superiority test for the Primary Endpoint fails, the testing procedure stops and no further testing will be performed.

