4.5.5 Patient Reported Outcomes

Hearing Aid Experience Questionnaire and the Nucleus 7 Questionnaire

These two device use questionnaires were developed by the Sponsor and are used to collect information regarding device usability, subjective preferences, and satisfaction with regards to device use in various listening conditions. The baseline is the Hearing Aid Experience Questionnaire and the follow-up is the N7 questionnaire completed at the 6 month interval. The differences between the N7 questionnaire and baseline (i.e. change in baseline) will be analyzed using a repeated measures, mixed effects model, with the device use difference as the response and variables such as speech perception, age and gender as the explanatory variables. Additionally, the proportion of subjects reporting being satisfied a score of >50 will also be reported.

Speech, Spatial, and Qualities of Speech Questionnaire (SSQ)

The SSQ is a close-ended questionnaire composed of several subjective questions related to quality of speech. The baseline and the follow-up SSQ at the 6 month interval will be recorded for each subject. The differences between the 6-month SSQ and baseline SSQ will be analyzed using a one-sample t-test of the paired difference in pre and post results and performed at the one-sided 0.025 alpha level. If there is significant evidence that the assumptions of the t-test do not hold (i.e. $p < 0.05$ from a Shapiro-Wilks test of normality), a Wilcoxon signed rank test will be used. Additionally, the differences between the 6-month SSQ and baseline SSQ (i.e. change in baseline) may be analyzed using a repeated measures, mixed effects model, with the SSQ difference as the response and variables such as speech perception, age and gender as the explanatory variables. To determine individual postimplant benefit for the categorization system developed by Noble et al. (2009) will be used (≤ 1 = no benefit; $>1-2$ = benefit; $>2-4$ = high benefit; >4 = very high benefit) with the proportion of subjects falling into each category will be reported.

Mini-Tinnitus Questionnaire (Mini TQ)

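### SAP 4.4 claims fixed-sequence control of type I error, but its written rule opens AzBio and HUI3 together at full alpha once CNC passes

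*SAP*

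**What the plan says.** SAP section 4.4 names the procedure and its scope: "The hypotheses for the primary and secondary Endpoints are to be tested formally according to a fixed sequence testing procedure". It states the purpose: "This testing procedure is based on the principle of a closed testing procedure and is used to control the type I error". It sets the level for every test: "In the fixed sequence testing, all the following superiority tests will be conducted using a two-tailed 95% CI", that is, one-sided 0.025.

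It then gives two operative rules. The first opens the secondaries: "Only if the superiority test for the Primary Endpoint is successful, then the secondary endpoints will be tested". The second is the only stop: "If the superiority test for the Primary Endpoint fails, the testing procedure stops and no further testing will be performed".

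Section 4.3.2 defines two formal secondary hypotheses. One is AzBio sentences at +10 dB SNR. The other is HUI3, introduced with "An additional secondary objective will be evaluated by comparing of the group mean for preoperative vs. 6 months postoperative health utility outcome". Each carries the same sentence on level: "All tests will be performed at the one-sided 0.025 alpha level". The CNC, AzBio and HUI3 nulls all bear the label H01, so the labels give no ranking.

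**The concern.** A fixed sequence may use the full alpha at every step because each hypothesis is tested only after all earlier ones have been rejected. That needs a complete order and a stop at every failure. Section 4.4 supplies the first link, CNC before the rest, and leaves out the second. An analyst who follows its text would test HUI3 at 0.025 even after AzBio failed, and could claim it.

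The appeal to closed testing does not fill the gap. Closure requires a level-0.025 test of the joint null that neither AzBio nor HUI3 improves. Under the written rule, once CNC has passed, that joint null is rejected whenever either test succeeds, which can happen with probability up to 0.05.

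At stake is the stated family-wise level for the secondary claims, and whether two analysts would draw the same claims from the same data when AzBio fails and HUI3 passes.

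**Working it through.** **Inputs from SAP section 4.1:**
- CNC: difference 15%, SD of differences 22.4%.
- AzBio: difference 15%, SD 21.3%.
- HUI: difference 0.12, SD 0.18.
- Two-sided 0.05 (one-sided 0.025), power 0.9, enrolment 100.

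**Assumed:** the correlation between the AzBio and HUI3 test statistics, which the SAP does not give. The range 0 to 0.9 is shown.

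**Step 1. Reproduce the plan's sample sizes.** A paired t-test with the exact noncentral t distribution, at one-sided 0.025 and 90% power, gives 26 (CNC), 24 (AzBio) and 26 (HUI). These match the SAP. Each secondary was therefore planned at the full 0.025, with no alpha split.

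**Step 2. How often the gate opens on planned effects.** With 100 evaluable subjects the CNC noncentrality is (15/22.4) × √100 = 6.70, and power is 0.999998. If the planned CNC effect is real, the secondaries are almost always tested.

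**Step 3. Error under the written rule, with CNC improved and both secondary nulls true.**

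P(at least one false claim) = 0.025 + 0.025 − P(both statistics exceed 1.96)

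If independent: 0.05 − 0.025² = 0.05 − 0.000625 = 0.0494. For other correlations the joint term comes from the bivariate normal distribution:

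| Assumed correlation | P(at least one false secondary claim) | Ratio to 0.025 |
|---|---|---|
| 0 | 0.0494 | 2.0 |
| 0.3 | 0.0476 | 1.9 |
| 0.5 | 0.0454 | 1.8 |
| 0.7 | 0.0417 | 1.7 |
| 0.8 | 0.0390 | 1.6 |
| 0.9 | 0.0352 | 1.4 |

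The upper bound for any correlation is 0.025 + 0.025 = 0.05.

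**Step 4. Simulation of the full rule.** There were 400,000 draws, with a common correlation among the three statistics.

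| Correlation | Written rule, CNC improved | Ordered with stops, CNC improved | Holm on the pair, CNC improved | Written rule, all three nulls true |
|---|---|---|---|---|
| 0 | 0.0495 | 0.0251 | 0.0251 | 0.0248 |
| 0.3 | 0.0472 | 0.0245 | 0.0239 | 0.0247 |
| 0.5 | 0.0452 | 0.0250 | 0.0232 | 0.0251 |
| 0.7 | 0.0413 | 0.0246 | 0.0212 | 0.0250 |

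The written rule holds 0.025 when all three nulls are true (weak control). It does not hold 0.025 when CNC improves and both secondary nulls are true, so strong control fails. Both alternatives hold it, to within simulation error.

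**Step 5. Power cost of a repair.** At n = 100 and one-sided 0.0125 (the first Holm step), power is 0.999999 for AzBio and 0.999993 for HUI. At that level, 90% power would need 28 subjects for AzBio and 31 for HUI, both far below 100.

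**The case against.** The strongest reply is that the name of the procedure already implies the missing rule. A fixed sequence, properly understood, is ordered and stops at each failure, and a full 0.025 per test is what such a sequence uses. An order can also be inferred: AzBio precedes HUI in section 4.1 and again in 4.3.2, where HUI3 is the additional objective. If AzBio then HUI3 was intended, with a stop after AzBio, the error is held at 0.025.

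Part of this stands. The repeated 0.025 is not a fault in itself, and the order may well have been meant. But the inferred order is nowhere called the testing order. The SAP spells out one stop, for the primary only, and opens the secondaries together. The rule as stated lacks the property claimed for it.

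It is also fair to say that the practical effect is limited. The inflation arises only if both secondary nulls are true; if just one is true, its error is 2.5% as written. On the planned effects all three tests would almost surely pass under any of these schemes.

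A reader might go further and count SSQ as a third test, since section 4.5.5 also gives it a "one-sample t-test of the paired difference in pre and post results and performed at the one-sided 0.025 alpha level". The SAP does not support that. Section 4.4 claims control for the primary and secondary endpoints, and SSQ sits among the additional analyses and is not called a secondary endpoint. It cannot breach a claim that does not cover it.

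**Conclusion.** Wrong as written; should be fixed. Section 4.4 claims type I error control across the primary and secondary endpoints, but its stated rule does not give strong control over AzBio and HUI3. With a true CNC effect and both secondary nulls true, the family-wise error is about 3.5% to 4.9% one-sided, or 1.4 to 2 times the claimed 2.5%. This rests on the literal reading of 4.4 and on an assumed correlation of 0.9 to 0.

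Two stronger conclusions might be inferred and do not follow. The gate is not worthless: it protects the CNC test and holds 0.025 when all three nulls are true. Nor is the error simply doubled: a factor of two is the limit, approached at independence, and the factor falls as the correlation rises. The primary conclusion is untouched.

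**What to change.** Amend section 4.4 in one of two ways:

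- **Fixed order.** Test CNC, then AzBio at +10 dB SNR, then HUI3, each at one-sided 0.025, stopping at the first failure. The cost is that HUI3 cannot be claimed if AzBio fails.
- **Holm after the gate.** If CNC passes, compare the smaller of the two secondary p-values with 0.0125. If it is significant, compare the larger with 0.025. The cost is the stricter first step.

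Either takes a sentence or two. On the plan's assumptions with 100 evaluable subjects, power for each secondary stays above 0.9999 even at 0.0125, so the sample size need not change. The choice should be made without reference to the 6-month secondary results.

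SSQ need not enter the sequence. At most, label its p-value nominal.

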4.5 Additional Statistical Analyses

4.5.1 Analysis of Demographic Characteristics

The demographic characteristics of the study group will be presented descriptively. Quantitative variables such as age, duration hearing loss and duration of severe to profound hearing loss will be presented with mean, standard deviation, median, minimum and maximum. Other demographic factors such as etiology and medical comorbidities will be tabulated for each subject.

4.5.2 Subgroup Analyses

The consistency of the primary endpoint will be examined across subgroups of subjects defined by the following baseline characteristics: age, gender, and duration of hearing loss, baseline CNC word scores, and existing medical comorbidities. Any significant difference between subgroups on endpoints will be explored with additional analyses. Additionally, for the analysis of age subjects will be stratified into 2 groups according to age at time of surgery: 1). <65 years and 2). ≥ 65 years. The effect of age may further be investigated by examining outcomes by decade.

Additional analyses will be completed to evaluate speech perception in quiet and noise at 6 months in the best bilateral listening condition – for most subjects this will be the bimodal condition (CI + contralateral hearing aid), and for others this will be the combined condition CI + Acoustic hearing (same ear) + contralateral hearing aid). Additionally, a subgroup analysis will be done for: Subjects using bimodal hearing and subjects using combined hearing. Differences between and within the subgroup will be evaluated.

Subgroup analysis will be done for: Subjects using hybrid hearing (acoustic + electric in the implanted and subjects using electric alone. Differences between and within the subgroup will be evaluated for primary and secondary endpoints.

The number of subjects falling into each group following surgery cannot be predicted consequently, sample size is not adjusted based on these subgroup analyses.

In addition, the consistency of the primary endpoint will be examined across investigational sites by testing for an effect of site in ANOVA model. Any potential variation between sites in the primary endpoint will be explored by assessing whether or not there are differences in baseline characteristics between subjects at sites that might explain the results.

Exploratory analyses may be conducted to determine factors that predict performance on a CNC word score at 6 months.

Factors that will be considered are:

- Demographic variables such as age, degree of hearing loss, duration of hearing loss
- Other preimplant variables such as: CNC word score, AzBio +10 score, AzBio +5 score, PTA, LFPTA, SSQ score, HUI score and MoCA score (pass/fail)
- Surgical factors, such as surgical approach, speed of insertion of sheath and electrode and number of white markers visible
- Electrode factors such as, electrode location, WF, basal angle of insertion and apical angle of insertion
- Post implant variables: hours of device use, CNC word score at 3 months, AzBio +10 at 3 months, HUI and SSQ scores at 6 months

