4.5.3 Change in Audiometric Thresholds

This is not a hearing preservation study and as such loss of low frequency hearing will not be tracked as an adverse event, changes in low frequency will be documented and reported. Specifically:

- The change in the low frequency pure tone average audiometric threshold in dB (125 Hz-750 Hz LFPTA) at each interval (IA, 1, 3, 6 and 12 months) will be calculated for each subject.
- The change in the audiometric threshold in dB at 500 Hz at each interval (IA, 1, 3, 6 and 12 months) will be calculated
- Additionally the effect of age on the change in LFPTA at each interval will be calculated. The effect of age will further be analyzed by stratifying the subjects into 2 groups based on their age at time of enrolment: <65 years of age and ≥65 years of age. Differences between and within the groups will be evaluated.

Additionally, the audiometric results will be reported according to the AAO Consensus on minimal reporting (Adunka, 2018)

These results will be documented in an Annual Progress Report and in publication(s).

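### For the primary endpoint, the only age analysis both committed and specified is a two-group cut at 65, and the same groups are dated at surgery in 4.5.2 but at enrolment in 4.5.3

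*SAP*

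**What the plan says.** Section 4.5.1 lists age among the "Quantitative variables such as age, duration hearing loss and duration of severe to profound hearing loss" to be summarised by mean, SD, median and range.

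Section 4.5.2 examines whether the primary endpoint is consistent across subgroups "defined by the following baseline characteristics: age, gender, and duration of hearing loss, baseline CNC word scores, and existing medical comorbidities". It then adds that "for the analysis of age subjects will be stratified into 2 groups according to age at time of surgery", namely under 65 and 65 or over. A further look is optional: "The effect of age may further be investigated by examining outcomes by decade". The same section allows an exploratory search for predictors of the 6-month CNC score, with candidates that include "Demographic variables such as age, degree of hearing loss, duration of hearing loss"; that search may be done, and no cut is stated for age.

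Section 4.5.3, on low-frequency thresholds, first says "Additionally the effect of age on the change in LFPTA at each interval will be calculated" and then "The effect of age will further be analyzed by stratifying the subjects into 2 groups based on their age at time of enrolment", again under 65 and 65 or over.

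Section 4.5.5 lists age, with no cut, as an explanatory variable in the mixed models for the patient-reported outcomes. The revision history (section 11.0) gives consistency with Medicare coverage as the reason for a boundary at 65.

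**The concern.** There are two separate issues.

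**Scale of age.** For the question of whether CNC benefit is consistent across age, the plan commits to one specified comparison: two groups split at 65. Read as a model, that comparison assumes no age effect within either group and a step at 65. If benefit changes gradually with age, the comparison discards part of what the recorded ages could show. A non-significant difference between the two groups could then be reported as consistency when the analysis was simply inefficient. The Medicare reason supports showing the split. It does not support making it the only committed age analysis.

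**Reference date.** The two sections build groups with the same labels from different dates. A subject who turns 65 between enrolment and surgery is in the younger group for low-frequency thresholds and the older group for CNC. The age-group sizes in one report need not agree, and a reader would have no explanation.

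**Working it through.** **Plan's own figure.** The SAP gives no figure for the age analyses. Its nearest one is the primary sample size: difference 15, SD of differences 22.4, two-sided alpha 0.05, power 0.90 (section 4.1). The normal approximation is [(1.960 + 1.282) × 22.4 / 15]² = 23.4, so 24. The paired t-test (noncentral t) gives 26, as stated. Nothing below alters it.

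**Information kept by a cut at 65.** Inputs: age normal with mean 60 to 70 and SD 12 to 15 (assumed; the SAP gives no age distribution), and a linear age effect (assumed). With z = (65 − mean)/SD and q the share aged 65 or over, the share of linear information kept is φ(z)² / [q(1 − q)].

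| Mean, SD | z | q | φ(z) | Kept | Lost |
|---|---|---|---|---|---|
| 65, either SD | 0 | 0.500 | 0.3989 | 0.637 | 36% |
| 60, 15 | 0.333 | 0.369 | 0.3774 | 0.611 | 39% |
| 60, 12 | 0.417 | 0.338 | 0.3658 | 0.598 | 40% |

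Mean 70 mirrors mean 60. If age were uniform instead, the share kept is 3q(1 − q): 0.75 at a 50/50 split and 0.6825 at 35/65, a loss of 25 to 32%.

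**Power.** Inputs: 95 subjects (assumed, from the 100 enrolled), SD of change 22.4 (section 4.1), age mean 67 and SD 14 (assumed), two-sided 0.05. A correlation of −0.30 (assumed) equals −0.30 × 22.4 / 14 = −0.48 points per year, or −4.8 points per 10 years. By Fisher's z, power = Φ[atanh(|r|√e) × √(n − 3) − 1.96]. Here e = 1 for age in years and 0.632 for the cut.

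- Age in years: atanh(0.30) × √92 = 2.97; less 1.96 = 1.01; power 84%.
- Cut at 65: 0.30 × √0.632 = 0.2385; atanh × √92 = 2.33; less 1.96 = 0.37; power 65%.

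Simulation of the same setting gives 83 to 85% and 65%. At r = −0.25 the formula gives 69% and 49%; at r = −0.20, 49% and 34%.

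**Decades.** For normal age (mean 60 to 70, SD 10 to 15), decade bands lose only about 4 to 8% of the linear information. In simulation at r = −0.30, a trend across decades has about 83% power. An unordered one-way ANOVA across the same bands has about 51 to 54%. The SAP names neither test.

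**Two dates.** Expected number changing group = 100 × age density at 65 × gap in years. For normal age with mean 60 to 70 and SD 10 to 15, about 2.5 to 4.0 subjects per 100 turn 65 in a year. A gap of 1 month (assumed) gives at least 2.5/12 = 0.2; a gap of 6 months (assumed) gives at most 4.0/2 = 2.0.

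**The case against.** The case on the other side is substantial, and most of it limits how far the point reaches.

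- **A reader might infer that the plan replaces age in years throughout.** The documents do not support that. In 4.5.2 the 65 split is introduced as an addition. In 4.5.3 it follows an age effect that is not tied to any grouping. The patient-reported outcome models in 4.5.5 list age with no cut. What remains is narrower. For change in CNC, the sentence before the split still speaks of subgroups and gives no scale, cut or model. The exploratory predictor search is optional, and its outcome is the 6-month score, not the change. In 4.5.3 the scale of age is unstated, not wrong.
- **A reader might extend the loss to decades.** That also fails. Decade bands keep nearly all the linear information, and low power would follow only from an unordered test that the plan does not name.
- **A reader might take a loss of more than a third as fact.** It depends on an age distribution and a linear effect that the SAP does not give. With uniform age the loss stays below a third.
- **A reader might conclude that an age trend is likely to be missed.** No trend is known to exist, and at an assumed correlation of −0.30 the cut would still detect it about 65% of the time.
- **The cut is prespecified, has a stated payer reason and sits among supportive analyses.** Section 4.5.2 says that the sample size is not adjusted for its subgroup analyses. This stands as a reason to keep the table and to rate the point low. It gives no reason to leave age in years uncommitted when the ages are already collected.

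**Conclusion.** The point holds in limited form. No committed analysis relates change in CNC to age in years; the only one both committed and specified is the split at 65. Under assumed normal age and a linear effect, the split loses about 36 to 40% of the age information (25 to 32% if age is uniform). With an assumed correlation of −0.30 and 95 subjects, power falls from about 85% to 65%. This does not extend to decade bands analysed as a trend.

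The conflict between the dates is plain in the text and needs no assumption: "for the analysis of age subjects will be stratified into 2 groups according to age at time of surgery" against "stratifying the subjects into 2 groups based on their age at time of enrolment". Its effect is small, about 0.2 to 2 subjects per 100 for an assumed gap of 1 to 6 months.

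The primary test, its sample size and the fixed testing sequence are untouched. This is a worthwhile improvement, not a flaw that threatens the trial's conclusions.

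**What to change.** 1. In 4.5.2, make the main age analysis a linear regression of change in CNC score on age in years. Report the slope per 10 years with its 95% CI, and check curvature. Keep under 65 versus 65 and over as the Medicare-related table.
2. In 4.5.3, state that the age effect on change in LFPTA uses age in years, with the 65 split shown alongside.
3. Choose one reference date for age, surgery or enrolment, and use it in both sections.

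The cost is SAP wording only. Age is already recorded, no new data are needed, and no planned table is lost.
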